7.2 Cohorts 2 & 3 Recruitment, Screening & Enrollment

Cohort 2 Recruitment and Enrollment: Participants for Cohort 2 will be individuals who are receiving HIV in care at BMC's Center for Infectious Diseases (CID) and are receiving CAB-RPV LA. CID pharmacists and providers will approach all individuals who are actively receiving CAB-RPV LA and assess whether they are interested in participating and ask them to complete the Screening Consent (Appendix C). If individuals are interested in participation, they will be given a warm handoff to study staff. Study staff will meet with patients at CID to complete the enrollment consent form (Appendix D). Participants will also be asked to complete the participant questionnaire at the baseline, midpoint (2-4 months post baseline) and endpoint (at least 6 months post baseline). They will also be asked to complete the Locator Form (Appendix F). Participants will enter the cohort and contribute data to the study from their first CAB-RPV LA injection and be followed in the EHR for a period at least 6 months to determine engagement in care and adherence. Data on clinical endpoints (appointment adherence, viral load, CD4, drug use etc.) will be collected from the EHR.

Cohort 3 Recruitment and Enrollment: EHR data will be used to match patients for Cohort 3 1:1 to patients in Cohort 1 based on the following variables: history of drug use, housing status, sex. Patients in cohort 3 will be a prospective cohort of patients who are HIV positive and not receiving CAB-RPV LA. The Clinical Data Warehouse will match 10 participants to every 1 enrolled in Cohort 1 based on the variables above. CID staff will approach potential participants to assess interest in participation. If individuals are interested in participating, they will be given a warm handoff to the project manager to complete the Enrollment Consent form (Appendix D). They will also be asked to complete the Locator Form (Appendix G). The remainder of their study activity will mirror that of Cohort 2.

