5.0 Study Subject Selection

5.1 Subject Inclusion Criteria

Cohort 1: Age \geq 18 years, English or Spanish speaking, HIV-positive, labs indicate that they are a candidate for the medication and virally suppressed, meaning that their HIV-1 ribonucleic acid is less than 50 copies per mL. Individuals enrolled in Cohort 1 must be willing to complete the locator form (Appendix G) in order to receive appointment reminders prior to their monthly/bi-monthly injection and ongoing follow-up by outreach and study staff to maximize potential for adherence.

Cohort 2: Currently enrolled in care at CID and receiving CAB-RPV LA injection, age \geq 18 years, English or Spanish speaking. Individuals enrolled must be willing to complete the locator form in order to receive appointment reminders prior to follow-up data collection.

Cohort 3: Enrolled in care at CID but not receiving CAB-RPV LA, age \geq 18 years, matched to participants demographically and in terms of other characteristics in Cohort 1 at a 1:1 ratio. Individuals in Cohort 3 will be receiving the Standard Care for HIV treatment in CID. Standard of care for this group includes access to regular appointments with their HIV provider, oral ART, case management services, etc. Individuals enrolled must be willing to complete the locator form in order to receive appointment reminders prior to follow-up data collection.

Our goal for all three cohorts is to enroll a percentage of women that is equivalent to the number of female patients served by the sites, approximately 20-30% female. Similarly, we will ensure that our sample includes individuals of color proportional to their representation within the setting across all three cohorts.

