6.0 Study Intervention

The study intervention for Cohort 1 is delivery of HIV medication at Project Trust, rather than in the BMC HIV Clinic. Project Trust (PT) is a street-based drop-in clinic that is focused on STD testing, treatment, harm reduction, and social services engagement. PT engages in outreach work, provides individuals with substance use disorder safe injection kits, and is a well-established community site for the target population frequenting the area, which is home to a high number of individuals who are homeless, diagnosed with substance use disorder, and are living with HIV. Study staff who will be administering the injection are all trained clinicians (either nurse practitioners or physicians) and are BMC staff. Individuals administering the injection will all be listed on the BUMC Internal Review Board study protocol.

There is not a clinical intervention or any intervention beyond data collection for Cohorts 2 or Cohort 3. Cohort 2 will be receiving their CAB-RPV LA within the BMC HIV clinic as their standard care. Cohort 3 will be receiving standard of care (not CAB-RPV LA) and will be patients of the BMC HIV clinic. Individuals enrolled in all three cohorts will be asked to complete a survey at study enrollment (baseline), between 2-4 months after their enrollment (midpoint) and a final follow up between 6 - 8 months post baseline. Clinical data will be obtained from the BMC EHR via the clinical data warehouse at these time periods and no other data will be collected directly from study participants for Objective 2.

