7.0 Study Procedures

Medication regimen

	Cohort 1	Cohort 2
Month 1	Optional Oral lead-in (up to 28 days) 30 mg tablet of Vocabria 25 mg tablet of Edurant Opt out of Oral Lead-In:	(Anticipated) Maintenance Dose

Protocol Title: **CAB-RPV LA Implementation Strategies for High-Risk Populations**

	Initiation Injection (600 mg of cabotegravir and 900 mg of Rilpivirine)	
Month 2	
Oral Lead-in Completed: Initiation dose (600 mg of cabotegravir and 900 mg of rilpivirine)
 
Oral Lead-in not done: Maintenance Dose (400 mg of cabotegravir and 600 mg of rilpivirine)
	Monthly: Maintenance Dose Bi-monthly: No Injection
Month 3	
Oral Lead In completed: Maintenance Dose (400 mg of cabotegravir and 600 mg of rilpivirine)
 
Oral Lead In Not Done: Monthly: Maintenance Dose Bi-Monthly: No Injection
	Monthly: Maintenance Dose Bi-Monthly: Maintenance Dose
Month 4	
Oral Lead In: Monthly: Maintenance Dose Bi-Monthly: No Injection
 
No Oral Lead In: Monthly: Maintenance Dose Bi-Monthly: Injection
	Monthly: Maintenance Dose Bi-monthly: No Injection
Month 5	
Oral Lead In: Monthly: Maintenance Dose Bi-Monthly: Maintenance Dose
 
No Oral Lead In: Monthly: Maintenance Dose Bi-Monthly: No Injection
	Monthly: Maintenance Dose Bi-Monthly: Injection
Month 6	
Oral Lead-In: Monthly: Maintenance Dose Bi-Monthly: No Injection
 
No Oral-Lead In: Monthly: Maintenance Dose Bi-Monthly: Injection
	Monthly: Maintenance Dose Bi-monthly: No Injection
Month 7	
Oral Lead In: Monthly: Maintenance Dose Bi-Monthly: Injection
 
No Oral Lead In:
	Monthly: Maintenance Dose Bi-Monthly: Injection

	Monthly: Maintenance Dose Bi-Monthly: No Injection	
--	---------------------------------------------------------------------	--

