If the participant chose's to not take the oral lead-in mediation, the participant will proceed directly to the initiation injection once they have completed all required lab work, including HIV labs confirming that they are virally suppressed (> 50 copies per mL), and a comprehensive metabolic panel. The participant and their clinician will determine a date for the initiation injection. As the medication will need to be obtained from the pharmacy, participants will not be able to receive their initiation injection on the same day as they are enrolled into the study.

- At the time of the injection, during the 15 minute waiting period, study staff will sit with the participant and remind them of the target date for the next injection. This date will be recorded in the study Log Book. The month following the initiation dose, participants receive a maintenance dose. Once the participant has received the maintenance dose, the participant and their clinician may discuss whether the participant would like to shift to receiving the injection every other month rather than every month. The clinician and the participant may choose whether to receive the injection every month, or every other month per CID standard of care and the medication package insert.
- One week prior to each scheduled injection date, study staff will contact participant via their preferred contact method determined on the Locator Form to confirm injection date and confirm with the community-based clinician administering the injection.
- One day prior to injection date, study staff will contact participant for reminder.

Below is a table that outlines when all evaluation activities occur:

Month	Cohort 1	Cohort 2	Cohort 3
1	
• Screening• Enrollment• Comprehensive Metabolic Panel• Baseline Data Collection• Participant may choose to take 28 days of Oral Lead-In medication• If participant opts out of the oral lead-in, they will receive their Initiation Injection during this time point	
• Screening• Enrollment• Baseline Data Collection	
• Screening• Enrollment• Baseline Data Collection
2	
• Oral lead-in: Initial Injection• No Oral Lead-In: Maintenance Dose		

Protocol Title: **CAB-RPV LA Implementation Strategies for High-Risk Populations**

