11.3 Statistical Methods

We will first conduct exploratory analyses to assess the completeness and distributional properties of all variables, including an exploration of location (e.g., means for continuous variables and frequencies and percentages for categorical variables), spread (e.g., ranges, standard deviations), and shape (e.g., normal, skew). Missing baseline sociodemographic data will be imputed using single or multiple imputation technique if the proportion missing is $<10\%$ or $\geq 10\%$, respectively. After enrollment, we will compare dropout rates and characteristics of subjects who drop out or are lost to follow-up to assess potential for bias. In cases of missing viral load data, we will treat the result as detectable, in accordance with our primary ITT analytic approach, similar to other studies. Our primary analyses will be by ITT, but we will also conduct per protocol analyses via logistic regression models to estimate treatment effects.

Sociodemographic, behavioral, and clinical attributes at baseline will be compared between Cohort 1 and Cohort 2 and Cohort 1 and Cohort 3 using Chi Square and Fisher Exact test for categorical variables and T-test and Wilcoxon and Kruskal-

Protocol Title: **CAB-RPV LA Implementation Strategies for High-Risk Populations**

Wallis tests for continuous variables. Differences in engagement in care will be examined in two separate models to compare Cohort 1 vs Cohort 2 and Cohort 1 vs. Cohort 3. We will construct a multivariable logistic regression model with a logit link and the events/trials syntax to model the outcome. The inclusion of key baseline variables for adjustment will be based on a p value of ≤ 0.2 in the bivariate analysis or clinical significance. The following regression equation will be used:

$$\text{Engagement in care} = \alpha + \beta_1 * \text{ixgroup}_1 + \beta_2 * \text{factor}_1 + \dots + \beta_n * \text{factor}_n + \varepsilon,$$

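### Section 7.2 starts Cohort 2's outcome data at the first injection but recruits from patients still on injections, while the rest of the protocol counts from enrolment

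*Combined protocol and SAP*

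**What the plan says.** Section 7.2 gives Cohort 2 its start date: "Participants will enter the cohort and contribute data to the study from their first CAB-RPV LA injection". The same sentence says they will "be followed in the EHR for a period at least 6 months to determine engagement in care and adherence". Recruitment is described in the same paragraph: "CID pharmacists and providers will approach all individuals who are actively receiving CAB-RPV LA". The inclusion criterion in section 5.1 agrees: "Currently enrolled in care at CID and receiving CAB-RPV LA injection". The medication table in section 7.0 anticipates that Cohort 2 is already on a maintenance dose in Month 1, so the first injection is expected to fall before enrolment.

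Other sections use a different clock:
- Section 6.0 times the surveys of all three cohorts from enrolment, ending with "a final follow up between 6 - 8 months post baseline", and takes the EHR data at the same time points.
- The evaluation table in section 7.1 puts Cohort 2's baseline in Month 1, its midpoint in Months 3 to 5 and its endpoint in Months 7 to 9, as for Cohort 1.
- Section 7.3 collects EHR endpoints at enrolment and at each later data collection.
- Section 10.1 reviews the EHR at 3 and 6 months after the eligibility review.

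Cohort 1 enrols before any injection. Section 7.1, on those who skip the oral lead-in, says that "participants will not be able to receive their initiation injection on the same day as they are enrolled into the study"; those who take the lead-in are injected later still. Section 11.3 examines engagement in "two separate models to compare Cohort 1 vs Cohort 2 and Cohort 1 vs. Cohort 3".

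**The concern.** Where follow-up starts before recruitment, the time between the two is survived by design. A clinic patient who started CAB-RPV LA and stopped before being approached cannot enter Cohort 2, yet the months before the approach count as outcome time for those who did enter. This is immortal-time, or prevalent-user, selection. Cohort 1 has no such protection, because a participant who enrols and then stops after one injection stays in the denominator.

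The Cohort 1 vs Cohort 2 contrast is the one that holds the drug constant and varies the delivery site, which is the implementation question. A selection effect in favour of clinic delivery could make community delivery look worse when the two sites perform equally. Adjusting for baseline covariates, as section 11.3 plans, cannot restore patients who never entered.

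If viral suppression is also compared between these cohorts, as the power text in section 11.2 suggests, the missing-data rule adds to the asymmetry. A Cohort 1 participant lost to care is scored as detectable. A clinic patient lost before consent is not in the data at all.

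**Working it through.** **Which clock applies.** Section 7.2 is the only place that says when Cohort 2 begins to contribute data. Nothing limits Cohort 2 to new starters, caps time since first injection, or removes pre-enrolment time. Sections 6.0, 7.1, 7.3 and 10.1 schedule collection from enrolment without overriding 7.2. Section 7.2 also has Cohort 3's remaining activities mirror Cohort 2's, although Cohort 3 has no injection to count from. Two analysts could therefore build different 6-month windows from the same protocol.

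**The plan's own figure.** The plan gives no figure for persistence or for time since first injection. Its sample size (20 per cohort, 90% vs 50%, 80% power, alpha 0.05) reproduces: the two-sided, pooled-variance calculation without continuity correction gives n = 20 and 81.3% power. The choice of clock does not change it.

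**Illustration of the selection.** Let S be the true probability of still being on injections 6 months after the first one, the same at both sites, with a constant drop-out rate. A patient approached k months after the first injection is known to have persisted to month k. Persistence counted from first injection then appears as

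P(on injections at month 6 | on injections at month k) = S^((6 − k)/6) for k ≤ 6, and 1 for k > 6.

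For S = 0.80: k = 2 gives 0.80^(4/6) = 0.862; k = 4 gives 0.80^(2/6) = 0.928; k = 6 or more gives 1.

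| True S (assumed) | k = 2 | k = 4 | k ≥ 6 | Excess over S, in points |
|---|---|---|---|---|
| 70% | 78.8% | 88.8% | 100% | 8.8, 18.8, 30 |
| 80% | 86.2% | 92.8% | 100% | 6.2, 12.8, 20 |
| 90% | 93.2% | 96.5% | 100% | 3.2, 6.5, 10 |

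In a cohort of 20 with S = 80%, the excess is 0.062 × 20 = 1.2, 0.128 × 20 = 2.6 or 0.20 × 20 = 4 patients.

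**With the clock at enrolment.** Under the same constant rate, 6-month persistence from enrolment is S in Cohort 2 whatever k is, so the artificial excess is 0. If drop-out is concentrated soon after starting, established users would still persist better than new starters, and the clock change would not remove that part.

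**The case against.** The strongest reply is that most of the protocol already uses an enrolment clock, for EHR data as well as surveys, so the sentence in 7.2 may be loose drafting. That has force: the documents show an inconsistency that could produce the bias, not a settled plan to score pre-consent months. But the sentence is explicit and names engagement and adherence as its purpose, so it has to be reconciled.

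Four stronger readings are tempting, and the documents do not support them.
- *Part or all of Cohort 2's engagement result is fixed before enrolment.* Section 11.2 equates engagement with appointment adherence, and 11.3 models it as events out of trials. A patient still on injections may have missed visits, so the outcome is selected for, not guaranteed. A window lying wholly before consent is also an inference, because 7.2 says at least 6 months.
- *The percentages above measure the bias in the planned model.* They describe injection persistence. The documents give neither the drop-out rate nor the recruitment lag, and approaching every active recipient brings in recent starters too.
- *The main hypotheses are compromised.* H3 and H4, the latter being the one the study is powered for, compare Cohort 1 with Cohort 3. H5 uses Cohort 2, but through questionnaires timed from enrolment.
- *The net comparison must favour the clinic.* Only this one selection effect has a known direction. Cohort 1 receives injection reminders and street outreach after missed doses, and is limited to suppressed people who return to enrol. These could push the other way.

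**Conclusion.** The concern holds as an inconsistent start of follow-up. If section 7.2 is followed as written, it puts persistence-selected, pre-consent time into Cohort 2's side of the planned Cohort 1 vs Cohort 2 engagement model, and into viral suppression if those cohorts are compared on it. The effect of this selection is to inflate Cohort 2. Its size for appointment adherence cannot be derived from the documents. The persistence illustration runs from about 3 to 30 points over assumed true persistence of 90% down to 70% and lags of 2 to 6 or more months, and it rests on a constant drop-out rate that is equal at the two sites.

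Because no numbered hypothesis depends on this clock, and the other sections already point to the remedy, this is a point that should be fixed rather than one that undermines the study.

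**What to change.** In section 7.2, replace the first-injection start with study enrolment for all Cohort 2 outcomes (engagement, viral load and survey), in line with sections 6.0, 7.1, 7.3 and 10.1. State that EHR data from before enrolment serve only to describe baseline. Abstract the date of first injection from the EHR, where section 10.1 says injections are recorded, and report time on CAB-RPV LA at enrolment. In section 11.3, describe Cohort 1 vs Cohort 2 as new starters vs established users, and say that the clock change does not remove this difference. Settle the wording before Cohort 2 outcomes are examined.

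The cost is a protocol wording change and the abstraction of one date; whether the chart review form already captures that date cannot be seen here. Sample size is unchanged. The downside is that Cohort 2's pre-enrolment months no longer count as outcome data.

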1.2 Rationale & Purpose

Our proposed implementation research is designed to evaluate a novel approach to engage individuals with HIV who are at the highest risk for not accessing care or adhering to treatment. We are not testing CAB-RPV LA; this is an approved drug. We are also not studying the drug nor are we studying it for a new population, new dosage or new route of administration. Rather, we are conducting an implementation study and propose to test implementation CAB-RPV LA in community-based settings.

Strategies to implement evidence-based interventions to end the HIV epidemic are urgently needed. Despite highly effective antiretroviral treatment (ART) for HIV infection and multiple effective prevention interventions, there are approximately 40,000 new HIV infections annually in the US (CDC, 2019). Two of the four pillars of the US Department of Health and Human Services "Ending the HIV Epidemic" initiative are to:

Protocol Title: **CAB-RPV LA Implementation Strategies for High-Risk Populations**

1) treat individuals with HIV rapidly and effectively to achieve viral suppression; and 2) prevent new infections by using evidence-based interventions (<https://www.cdc.gov/endHIV/>).

Our implementation research addresses three ViiV Healthcare priority areas: 1) implementation of CAB-RPV LA delivery models in non-HIV clinic settings; 2) feasibility and acceptability of bringing CAB-RPV LA injections to the patient (rather than bringing the patient to the medication in more traditional ways only); and 3) addressing challenges of CAB-RPV LA delivery amongst high risk populations, specifically women and men of color, immigrants, homeless individuals, active substance users, transactional sex workers, individuals released from incarceration, and individuals who have fallen out of HIV care. Our study (which overall incorporates three Objectives) addresses the following research questions:

A. Implementation Questions

1. Will community-based delivery of CAB-RPV LA be an acceptable and feasible delivery method to high-risk PLWH from the patient, provider and community organization perspectives? (acceptability/feasibility)
2. Can a community-based delivery strategy lead to initiation and completion of injections for six months for at least 80% of individuals who are enrolled into Cohort 1 for an initial visit in an outreach setting? (reach)

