7.3 Data Collection

Objective 2 will include two forms of data collection: 1) participant questionnaires at enrollment (baseline), midpoint (2-4 months), and endpoint (at least 6 months post enrollment) follow-up; 2) clinical and appointment data from the EHR. The baseline questionnaire will be administered to all participants at the time of consenting to participate in the study in order to collect basic sociodemographic characteristics, such as gender identity, education, marital status, income, residence, and other characteristics shown to influence ART outcomes (Mills et al., 2006). The questionnaire will also collect data on potential predictors of intervention success, including unmet needs, satisfaction with care and stigma. (Appendix F). At the midpoint (2-4 months post enrollment) and endpoint (at least 6 months post enrollment), the data will be collected again, using the same data collection instrument. The midpoint data collection and endpoint data collection target dates will be determined by study staff and participants at the first enrollment appointment. For Cohort 1 and Cohort 2 participants, these dates will coincide with their scheduled injections if possible, for convenience.

One week before each target data collection date, study staff will contact the participant using the preferred communication method they specified on their Locator Form at enrollment. Once a data collection date has been determined, study staff will contact participant through their preferred means of communication one day prior to appointment for a reminder.

At the time of data collection, the participant and study staff will meet at determined study location (either Project Trust or CID). Study staff will bring the Participant Folder, Log Book and a ClinCard. The participant will complete the participant survey. If the participant is in Cohort 1 or 2 and is scheduled to receive their

Protocol Title: **CAB-RPV LA Implementation Strategies for High-Risk Populations**

injection at this appointment, the survey can be completed during the 15-minute observation period after the injection.

The clinical and appointment data to be collected from the EHR on all study participants will include clinical endpoints (appointment adherence, viral load, CD4, etc.). Data on clinical endpoints will be collected from their EHR at enrollment at each data collection period using the Chart Review Tool (Appendix E).

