7.11 Clinical Management of Participants

Many patients will already be Boston Medical Center patients, and will continue to see their usual Infectious Disease provider during the entirety of the study. Clinical decisions

Protocol Title: **CAB-RPV LA Implementation Strategies for High-Risk Populations**

around patients and the clinical management of missed doses, serious adverse events and adverse events will be managed by the Infectious Disease clinical providers who are on the study staff. Participants who are new to Boston Medical Center will have a new patient MRN assigned to them, and will be assigned to the clinical patient panel of one of the CID providers on the study staff. All clinical decisions about patients will be made by their healthcare providers. Whether to continue or discontinue Cabenuva if a participant becomes pregnant will be decided by the study clinicians in collaboration with the participant's CID provider that will also include a full review of the participant's case and medical record. All participants will continue to be offered all their regular services as before, including care in the CID, relapse prevention and harm reduction services, STI education and counseling, and all other needed services. Study staff will monitor for depression using the same procedures as CID.

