11.0 Statistical Plan

11.1 Study Hypotheses

Objective 2 has the following hypotheses:

- **H1:** Changing the service site will result in $\geq 80\%$ of participants in the community-based intervention arm beginning injections
- **H2:** Of participants in the community-based intervention arm who begin injections, 80% will complete 6 injections
- **H3:** Changing the service site will result in improved engagement in care for participants in the community-based intervention arm compared to matched controls (Cohort 3) at 6 months for intervention patients compared to control group patients
- **H4:** Changing the service site will result in superior HIV viral suppression at 6 months compared to for participants in the community-based intervention arm compared to matched controls (Cohort 3)
- **H5:** Participants in the community-based intervention arm will be equally satisfied with their care compared to patients who receive care in clinic settings (Cohort 2).

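### The H3 comparison of engagement in care does not match on, or require adjustment for, engagement before enrolment, although the two cohorts may start at different levels.

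*Combined protocol and SAP*

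**What the plan says.** H3 in section 11.1 states: "Changing the service site will result in improved engagement in care for participants in the community-based intervention arm compared to matched controls (Cohort 3" (the bracket then closes, and the comparison is set at 6 months). Section 11.2 equates engagement with appointment adherence.

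The two cohorts come from different places.

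- **Cohort 3** (section 5.1) is "Enrolled in care at CID but not receiving CAB-RPV LA". Section 7.2 has the Clinical Data Warehouse propose ten candidates per Cohort 1 participant, after which "CID staff will approach potential participants to assess interest in participation".
- **Cohort 1** (section 7.1) is recruited at a street drop-in site, a substance-use urgent care clinic at the medical center, and the lunch service of a programme for people living with HIV. It may include people treated elsewhere. Section 1.2 counts among the target groups "individuals released from incarceration, and individuals who have fallen out of HIV care".
- Cohort 1 must have a viral load below 50 copies per mL (section 5.1). Section 5.2 exempts Cohort 3 from the suppression requirement.

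Section 5.1 describes Cohort 3 as "matched to participants demographically and in terms of other characteristics in Cohort 1 at a 1:1 ratio" without naming those characteristics. The only named list is in section 7.2, where matching is "based on the following variables: history of drug use, housing status, sex".

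Section 11.3 models engagement by multivariable logistic regression with a cohort indicator. Baseline factors are added if their bivariate p value is at most 0.2 or if they are clinically significant. No covariate is named as required, and there is no change-from-baseline term. Section 7.3 lists appointment adherence among the clinical endpoints and says: "Data on clinical endpoints will be collected from their EHR at enrollment at each data collection period".

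**The concern.** The baseline value of an outcome is usually its strongest single predictor. In a non-randomised comparison it is also the first thing to balance or adjust for. Here one cohort is defined by being in clinic care. The other is found outside that clinic but must be suppressed at entry. Either could have the better recent attendance record.

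If they differ and the difference is not adjusted for, the 6-month contrast combines any effect of changing the service site with the gap that was already there. A real gain in Cohort 1 could be hidden, or an apparent gain could appear without an effect. H3 claims improvement relative to controls, and a 6-month level alone cannot separate improvement from a head start. The plan appears to collect the variable needed but leaves its use to a screening rule.

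**Working it through.** **1. The plan's own figure.** Section 11.2 states 20 per cohort, 90% vs 50%, 80% power, alpha 0.05. With the usual two-sided formula, without continuity correction:

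n = [1.96·√(2·0.7·0.3) + 0.8416·√(0.9·0.1 + 0.5·0.5)]² / 0.4² = (1.270 + 0.491)² / 0.16 = 19.4, so 20 per cohort.

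Power at 20 per cohort is 81.3%. The figure reproduces. It assumes comparable groups, so it does not bear on a starting gap.

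**2. How often the p ≤ 0.2 screen would admit prior engagement.** Section 11.3 introduces the screen directly after describing chi-square and Fisher comparisons between cohorts, so I read it as a between-cohort test. Treat prior engagement as yes/no, with 20 per cohort. Enumerate all pairs of binomial counts and sum the probability of those with p ≤ 0.2. The true rates are assumptions.

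| True prior engagement | Admitted, chi-square | Admitted, Fisher | Missed |
|---|---|---|---|
| 50% vs 60% | 29% | 17% | 71% to 83% |
| 50% vs 70% | 53% | 38% | 47% to 62% |
| 50% vs 80% | 80% | 68% | 20% to 32% |

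The screen could instead mean a test of each factor against the outcome. The same enumeration with 20 previously engaged people and 20 others, engaged at 6 months at 80% and 40%, admits the factor 93% (chi-square) or 86% (Fisher) of the time. The plan does not say which test is meant.

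**3. What a missed gap does.** Let q₁ and q₃ be prior engagement in Cohorts 1 and 3. Let h and l be 6-month engagement in previously engaged people and in others, with no intervention effect. The crude difference is then (q₁ − q₃)·(h − l). All inputs are assumed.

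- h = 80%, l = 40%; 50% vs 60% prior: 60% − 64% = −4 points.
- Same h and l; 50% vs 70%: 60% − 68% = −8 points.
- Same h and l; 70% vs 50%: 68% − 60% = +8 points.
- A steeper relation, h = 90%, l = 30%: −6, −12 and +12 points for the same three pairs.

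**4. Set against the design effect.** Section 11.2 claims power for engagement as well as viral load. With controls at 50%, a 40-point contrast reduced by 4 or 8 points becomes 36 or 32 points. By the formula in step 1, power at 20 per cohort falls from 81% to 70% or 57%.

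**The case against.** The strongest reply is that the plan already has an adjustment rule. The H3 model is multivariable, baseline attributes are compared first, and prior engagement may enter either by its p value or on clinical grounds. That stands: adjustment is optional, not excluded. A reader might infer that H3 will be analysed unadjusted, and section 11.3 does not support that. The rule still does not secure the adjustment. On the between-cohort reading it misses a 20-point gap about half the time or more, and clinical significance is undefined.

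A reader might also infer that the bias runs against the intervention because Cohort 1 comes from outreach. The documents fix no direction. Cohort 1 alone must be suppressed, must complete screening tests and must return to enrol, and section 7.11 says "Many patients will already be Boston Medical Center patients".

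It is also tempting to say that Cohort 3 is selected on the H3 outcome itself. Being enrolled in care is a status, while the outcome is the share of appointments kept. A poor attender can be enrolled, and nothing says the approach happens only at a kept visit.

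Two further points stand in part. H3 is not the powered hypothesis (section 11.2 names H4) and this is a pilot, which limits the weight of the point. The sentence in section 7.3 on collection at enrolment gives no look-back window, and section 10.1 describes the early record review mainly in terms of eligibility labs. The baseline measure therefore has to be defined as well as named.

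**Conclusion.** The point holds as a gap in pre-specification. Prior engagement is neither matched nor a required covariate in the H3 model, and the two cohorts' entry routes give reason to expect a difference of unknown sign. On the between-cohort reading, the screen would miss a true 50% vs 70% gap 47% to 62% of the time. A missed gap of 10 to 20 points would move the contrast by about 4 to 8 points in either direction on the main assumed rates, or 6 to 12 on a steeper relation. These sizes rest on assumed prior-engagement and follow-up rates, on a yes/no measure of prior engagement, and on reading the screen as a between-cohort test. The documents supply no rates. Larger biases need larger gaps or steeper relations than these, and nothing in the documents supports a particular value.

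**What to change.** In section 11.3, make baseline appointment adherence a fixed covariate in the Cohort 1 vs Cohort 3 engagement model, whatever the p ≤ 0.2 screen shows. Take it from the EHR and state the look-back window (for example, the 12 months before enrolment) in section 7.3.

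For Cohort 1 members without appointment history at the medical center, use outside records where these show kept appointments. Add a sensitivity analysis restricted to participants with prior history there. Do not add an indicator for being new to the center. It would be essentially zero throughout Cohort 3, so the cohort coefficient would then compare only established Cohort 1 patients with Cohort 3 and change the question.

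Using prior adherence in the warehouse match is optional and feasible only where history exists. It would make some matches harder to find.

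The cost is one model degree of freedom in a small sample, one defined extraction from the record, and incomplete baseline data for participants new to the center. The outside records are requested for eligibility screening and may not contain appointment counts.
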